9.2.5 Adverse Events

Adverse events, whether in response to a query, observed by site personnel, or reported spontaneously by the subject will be recorded. Adverse events definition and serious adverse event categories are described in detail in Section 11.0.

9.2.6 Removal of Subjects from Therapy or Assessment

1. Discontinuation of Individual Subjects

A subject may withdraw from the study at any time. The Investigator may discontinue any subject's participation for any reason, including an adverse event, safety concerns or failure to comply with the protocol.

Subjects will be withdrawn from the study immediately if any one of the following occurs:

- Clinically significant abnormal laboratory result(s) or adverse event(s), as determined by the Investigator in consultation with the AbbVie Medical Monitor.
- The Investigator believes it is in the best interest of the subject.
- The subject requests withdrawal from the study.
- Inclusion and exclusion criteria violation was noted after the subject started study drug, when continuation of the study drug would place the subject at risk as determined by the AbbVie Medical Monitor (see *Section 5.2 and Section 7.0*).

- Introduction of prohibited medications or dosages when continuation of the study drug would place the subject at risk as determined by the AbbVie Medical Monitor.
- Subject is non-compliant with TB prophylaxis.
- The subject becomes pregnant while on study medication.
- Subject has dysplasia of the gastrointestinal tract or a malignancy, except for localized non-melanoma skin cancer. Discontinuation for carcinoma in-situ of the cervix is at the discretion of the Investigator.
- Subject is diagnosed with lupus-like syndrome, multiple sclerosis or demyelinating disease.
- Subject is significantly non-compliant with study procedures which would put the subject at risk for continued participation in the trial, as determined by the Investigator, in consultation with the AbbVie Medical Monitor.

Following discontinuation of the study drug, the subject will be treated in accordance with the Investigator's best clinical judgment. A final phone call will be made to the subject approximately 70 days after the last dose of study drug to determine the status of any ongoing AEs/SAEs or the occurrence of any new AEs/SAEs.

For subjects that are considered lost to follow-up, reasonable attempts should be made to obtain information on the final status of the subject.

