9.0 Research Methods

9.1 Study Design

This study is designed as a prospective, observational study to assess the effect of adalimumab on health-related QoL and work productivity in patients with RA in China in clinical practice.

The study population will include Chinese adult patients with a diagnosis of RA who meet the requirements per the local label for treatment with adalimumab at the baseline visit. The decision to prescribe adalimumab for RA should be based on clinical practice criteria without taking participation in this study into account. Patients will be included in the study after a physician's decision of initiating Humira.

Approximately 52 patients diagnosed with RA that meet the inclusion and exclusion criteria will be enrolled at approximately 16 sites.

This study is non-interventional and the subjects/investigator will follow the current clinical practice in each site. Not additional task will be required other than current practice to keep the data as "real world data collect".

The observation period for each patient is 24 weeks. All visits are to be scheduled as per routine clinical practice, regardless of study participation. Patients may discontinue adalimumab treatment or the study at any time without prejudice.

The physician will follow the patient during regular clinic visits at intervals as determined by routine clinical practice. Data at the clinic visits within ± 7 days of the study-defined time points will be collected and data at the clinic visits closest to the study-defined time points will be used for statistical analysis (If there are 2 clinic visits equidistant from a study-defined time point which do not correspond to any other visit, data from the EARLIER clinic visit shall be used for the study-defined time point).

The HAQ DI data will be collected at baseline, Week 12 and Week 24 after treatment initiation with adalimumab, as per standard daily clinical practice. In addition, when available, other PROs of work activity and well-being, including the WPAI, EQ-5D, and SF-36, will also be collected.

The HCRU will also be collected, when available. This includes surgical procedures, hospitalizations, bed days in hospital, physician consultations etc. Costs will be assigned based on the HCRU using standardized costs for each participating countries.

Primary Endpoint

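### Protocol 9.2.6 ends study follow-up for an adverse event, laboratory result or TB-prophylaxis lapse even if adalimumab continues, so Week 24 HAQ DI can be lost in the primary group (minor)

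*Protocol*

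**What the plan says.** Protocol 9.2.6 lists ten events and introduces them with "Subjects will be withdrawn from the study immediately if any one of the following occurs". Two matter here:

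- "Clinically significant abnormal laboratory result(s) or adverse event(s), as determined by the Investigator in consultation with the AbbVie Medical Monitor"
- "Subject is non-compliant with TB prophylaxis"

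Neither mentions whether adalimumab continues. By contrast, the bullets on eligibility violations and prohibited medication apply only where continuing the drug would put the subject at risk. The text after the list covers only patients who have stopped: "Following discontinuation of the study drug, the subject will be treated in accordance with" the investigator's judgement, and "A final phone call will be made to the subject approximately 70 days after the last dose of study drug".

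Other sections bear on the same patient:

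- Protocol 9.8.2 counts as a reportable deviation any subject who met withdrawal criteria and was not withdrawn.
- Protocol 9.1 names two separate exits ("Patients may discontinue adalimumab treatment or the study at any time without prejudice") and leaves visits to routine care ("All visits are to be scheduled as per routine clinical practice, regardless of study participation"). Section 12.5 says the study does not intervene in drug treatment.
- The primary endpoint (9.7.4) is the Week 24 change in HAQ DI in patients continuing on adalimumab. The note closing the endpoint list in 9.1 defines not continuing by missed injections only: 2 consecutive, or 3 non-consecutive within 24 weeks.
- Table 1 schedules a HAQ at early termination or drop-out. The Week 24 visit has a window of ±7 days.
- Protocol 9.7.10 and SAP 3.5.5 impute nothing beyond questionnaire items and, in the SAP, missing days in dates.

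**The concern.** The withdrawal rule ends observation, and nothing in the plan makes it end treatment. A patient with a clinically significant laboratory abnormality that resolves, or a lapse in TB prophylaxis that is then corrected, could reasonably stay on adalimumab under routine care. By the injection rule that patient is still continuing, and so belongs to the population the primary endpoint describes. The protocol nevertheless removes the patient from the study, and a site that keeps observing records a deviation.

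The lost value is not a random omission. A clinical event after baseline triggers it, so the missing Week 24 values may differ systematically from those observed. The primary mean, the Week 24 responder rate and the other Week 24 PRO changes all use the same as-observed patients. Section 9.9 warns of missing data as a limit on what can be obtained. These data could be obtained at visits that take place anyway, but the protocol stops collecting them.

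**Working it through.** **1. The plan's own sample size.** Inputs from Protocol 9.5: mean change −0.21, SD 0.5, two-sided 0.05, 80% power, 10% dropout, N = 52. A paired t-test (noncentral t) needs 47 evaluable patients. 47 × 1.10 = 51.7, which rounds up to 52; dividing instead gives 47 / 0.90 = 52.2, or 53. With 52 × 0.90 = 46.8 evaluable, power is 79.6% at n = 46 and 80.5% at n = 47. The stated figure reproduces.

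**2. What happens to a patient withdrawn under 9.2.6 while still on adalimumab.**

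| Question | Governing text | Answer |
|---|---|---|
| Must the patient leave the study? | 9.2.6, 9.8.2 | Yes; staying is a deviation |
| Does adalimumab stop? | 9.1, 12.5 | Not determined by the study |
| Continuing on adalimumab? | 9.1 note | Yes, unless the injection rule is met |
| Is a Week 24 HAQ collected? | Table 1 | Only an exit HAQ, dated at exit |
| Is the gap filled? | 9.7.10, SAP 3.5.5 | No |

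**3. How often the exit HAQ serves as Week 24.** Week 24 is day 168, so the window is days 161 to 175. If exit is equally likely on each of days 1 to 168 (an assumption), the exit HAQ falls in the window on days 161 to 168, that is 8 / 168 = 4.8% of exits.

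**4. Power.** The documents give no rate for this kind of withdrawal, so 0 to 3 patients out of 47 is an assumption. At 0.21 / 0.5:

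| Evaluable | 47 | 46 | 45 | 44 |
|---|---|---|---|---|
| Power | 80.5% | 79.6% | 78.7% | 77.7% |

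This is about one point per patient, and only for losses beyond the 10% allowance.

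**5. Shift in the primary mean.** Let the true mean over all 47 be −0.21, let k patients be lost, let w = k/47, and let d be the mean change of those lost. The analysed mean is (−0.21 − w·d) / (1 − w). For k = 3 and d = +0.21 this is (−0.21 × 47 − 3 × 0.21) / 44 = −10.50 / 44 = −0.2386.

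| k | d = −0.42 | d = −0.21 | d = 0 | d = +0.21 |
|---|---|---|---|---|
| 1 | −0.2054 | −0.2100 | −0.2146 | −0.2191 |
| 2 | −0.2007 | −0.2100 | −0.2193 | −0.2287 |
| 3 | −0.1957 | −0.2100 | −0.2243 | −0.2386 |

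At k = 3 the shift runs from +0.014 to −0.029. The 95% CI half-width at n = 47 is t(0.975, 46) × 0.5 / √47 = 0.147, so the largest shift is 0.029 / 0.147, about one fifth of it. The sign depends on d, about which the documents say nothing.

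**The case against.** The strongest reply is that the patient in question is inferred. The heading of 9.2.6 speaks of removal from therapy or assessment, the closing text starts from drug discontinuation, and the phone call is timed from the last dose. Neighbouring triggers (pregnancy, malignancy, demyelinating disease) read as drug-safety stops. The sentence in 9.1 on stopping treatment or the study concerns the patient's freedom to leave; it does not show that anyone withdrawn for safety stays on drug. This stands as to frequency: the authors probably expected the drug to stop, and few or no patients may be affected. It does not remove the rule, because no sentence makes drug stop a condition and this study cannot impose one.

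It is also fair that Table 1 plans an exit HAQ without limiting it to the drop-out situations in 12.6, so these patients need not leave without any outcome. That value is seldom a Week 24 value. The CRF is a separate document that was not available, so drug status at exit may already be recorded.

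A reader might infer that the protocol and SAP put the same patient in different groups, and that this moves the primary result. The documents do not support that. In SAP 2.3 and 5.3 the term withdrawal population stands in brackets after patients already described as not continuing on adalimumab; it labels that group and does not widen it. A patient with no Week 24 HAQ is absent from the paired analysis under either label, so any effect on the primary mean comes from missing data.

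A reader might also extend the point to the trigger "The Investigator believes it is in the best interest of the subject". That is a matter for the investigator's discretion and should stay so.

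**Conclusion.** The point holds as a minor one. For two triggers (adverse event or laboratory result, and TB-prophylaxis non-compliance), following the protocol as written can stop Week 24 collection in a patient who is still in the primary group, for a reason tied to that patient's clinical course. The number is unknown and may be near zero, and the direction of bias is unknown. For 1 to 3 patients, an assumption without a source in the documents, the mean moves by 0.029 or less against a half-width of 0.147, and power falls by about one point for each loss beyond the 10% allowance. These shifts also assume that those lost change on average by between −0.42 and +0.21.

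It would be wrong to conclude that the primary result is in danger. Nothing in the documents suggests enough such withdrawals to alter it.

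**What to change.** In Protocol 9.2.6, state that a patient who meets the adverse-event, laboratory or TB-prophylaxis trigger, remains on adalimumab and does not withdraw consent stays under observation. Collect the Week 12 and Week 24 questionnaires and injection status at that patient's routine visits, unless the investigator judges that further data collection is not in the patient's interest. Reword the matching deviation bullet in 9.8.2 so that this observation is not a deviation, and report how many patients it concerns.

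Two small wording changes go with this: add withdrawal by the investigator to 12.6, and cite the missed-injection rule from Protocol 9.1 beside the withdrawal-population label in SAP 2.3 and 5.3.

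The cost is an amendment and a few extra questionnaires, possibly none. Treatment decisions, safety reporting and the handling of patients who stop adalimumab do not change.

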9.3 Variables

Variables:

Primary Variable

- Change in HAQ DI score at week 24 from the baseline

Secondary Variable

- Change in HAQ DI score at week 12 from the baseline
- Change in other PROs (SF-36 domain scales, EQ-5D Index, Work Productivity and Activity Impairment Questionnaire [WPAI]) from baseline to weeks 12 and 24
- Number and percent of patients achieving a clinically meaningful improvement on the HAQ DI, from baseline to weeks 12 and 24

Additional Secondary Variable

- Change in HAQ DI score from baseline to week 24
- Changes in the disease severity and PROs from baseline to week 24
- Healthcare Resource Utilization (HCRU) at baseline, weeks 12 and 24

Exploratory Variable

- Change in patient satisfaction questions from baseline to weeks 12 and 24
- Patient's impression of change at weeks 12 and 24 from baseline

9.4 Data Sources

Case Report Forms (CRFs) and patient questionnaires.

Collection of data includes but not limited to subject demographics, clinical history, comorbidities, spontaneous adverse events, and concomitant medications. The following questionnaires will be utilized to collect data directly from participating subjects:

- EQ-5D
- SF-36
- HAQ DI
- WPAI
- HCRU
- Patient Global Impression of Change (PGIC)
- Patient Treatment Satisfaction Questions

9.5 Study Size

Approximately 52 patients diagnosed with RA will be recruited. The planned sample size provides 80% power for detecting a statistically significant improvement in HAQ-DI (Δ HAQ-DI < 0) assuming a mean Δ HAQ-DI of -0.21 and a standard deviation of 0.5 (reference 11), at two-sided significance level of 0.05 and accounting for a 10% dropout rate. The sample size also provides 99% power for detecting a statistically significant clinically meaningful improvement in HAQ-DI (Δ HAQ-DI < -0.22) assuming a mean Δ HAQ-DI of -0.5 and a standard deviation of 0.7, at two-sided significance level of 0.05 and accounting for a 10% dropout rate.

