2. Participation in any RA-related clinical trial at the time of enrolment, at baseline or at any point during the past 24 weeks prior to baseline
3. Patients, who in the clinician's view, may not be able to accurately report their QoL or prior resource utilization
4. Patients, who in the clinician's view, may not be able to adhere to adalimumab therapy over 24 weeks.

Variables:

Primary Variable

- Change in HAQ DI score at week 24 from the baseline

Secondary Variable

- Change in HAQ DI score at week 12 from the baseline
- Change in other PROs (SF-36 domain scales, EQ-5D Index, Work Productivity and Activity Impairment Questionnaire [WPAI]) from baseline to weeks 12 and 24
- Number and percent of patients achieving a clinically meaningful improvement on the HAQ DI, from baseline to weeks 12 and 24

Additional Secondary Variable

- Change in HAQ DI score from baseline to week 24
- Changes in the disease severity and PROs from baseline to week 24
- Healthcare Resource Utilization (HCRU) at baseline, weeks 12 and 24

Exploratory Variable

- Change in patient satisfaction questions from baseline to weeks 12 and 24
- Patient's impression of change at weeks 12 and 24 from baseline

Data Sources: Case Report Forms (CRFs) and patient questionnaires. Collection of data includes but not limited to subject demographics, clinical history, comorbidities, spontaneous adverse events, and concomitant medications. The following questionnaires will be utilized to collect data directly from participating subjects, when applicable:

- EQ-5D
- SF-36
- HAQ DI
- WPAI
- HCRU
- Patient Global Impression of Change (PGIC)
- Patient Treatment Satisfaction Questions

Study Size: Approximately 52 patients diagnosed with RA that meet the inclusion and exclusion criteria will be enrolled at approximately 16 sites. The planned sample size provides 80% power for detecting a statistically significant improvement in HAQ-DI (Δ HAQ-DI < 0) assuming a mean Δ HAQ-DI of -0.21 and a standard deviation of 0.5

(reference 11), at two-sided significance level of 0.05 and accounting for a 10% dropout rate. The sample size also provides 99% power for detecting a statistically significant clinically meaningful improvement in HAQ-DI ($\Delta\text{HAQ-DI} < -0.22$) assuming a mean $\Delta\text{HAQ-DI}$ of -0.5 and a standard deviation of 0.7, at two-sided significance level of 0.05 and accounting for a 10% dropout rate.

Data Analysis:

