9.7.4 Primary Endpoint Analysis

The primary endpoint variable will be the change in HAQ DI score at week 24 after the initiation of adalimumab, in those patients continuing on adalimumab.

The objective of the primary endpoint analysis will be to demonstrate that treatment with adalimumab improves functioning as measured by the HAQ DI in subjects with RA following treatment initiation. This change will be summarized as the mean and 95% confidence interval and will be tested with a paired t-test.

The primary analysis will be summarized as the mean and 95% confidence interval and will be tested with a paired t-test without adjusting for baseline disease severity. For sensitivity analysis, the mean change in HAQ DI at week 24 will be analyzed using ANOVA adjusting for baseline disease severity.

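### The stated 99% power to show a mean HAQ-DI change beyond -0.22 is about 76% on the protocol's own inputs; 99% fits a test against zero

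*Protocol*

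**What the plan says.** Protocol 9.5 makes two power statements for one sample size: "Approximately 52 patients diagnosed with RA will be recruited".

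- The first: "The planned sample size provides 80% power for detecting a statistically significant improvement in HAQ-DI". Its bracketed condition is a change below 0, with an assumed mean of -0.21 and SD 0.5.
- The second: "The sample size also provides 99% power for detecting a statistically significant clinically meaningful improvement in HAQ-DI". Its bracketed condition is a change below -0.22, with an assumed mean "of -0.5 and a standard deviation of 0.7, at two-sided significance level of 0.05 and accounting for a 10% dropout rate".

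Both statements stand in the same form in the Abstract (4.0, Study Size). SAP section 4 does not carry the 99% statement.

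On the analysis side, Protocol 9.7.4 says: "The primary analysis will be summarized as the mean and 95% confidence interval and will be tested with a paired t-test". The aim given there is to show that functioning improves, which is a comparison with no change. SAP 5.3 plans a paired t-test or a Wilcoxon signed-rank test of the change. In the planned analyses (Protocol 9.7.5, SAP 2.2 and 5.3), -0.22 appears only as a cut-off for counting individual patients who improved, reported as number and percent.

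**The concern.** The two sentences have the same structure, and the bracket in each names the value the mean change must beat: 0 in the first, -0.22 in the second. Read that way, the second promises near-certainty of showing that the average improvement exceeds the clinically meaningful threshold. The assumed mean, however, lies only 0.28 beyond the threshold with an SD of 0.7, and some 47 patients cannot give 99% power for that.

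The statement bears on how a result would be read. At 99% power, failure to show a mean change beyond -0.22 would look like strong evidence against a meaningful benefit. At about 76%, it would be a fairly ordinary outcome even if the sponsor's assumptions were true. The claim also makes the design look stronger than it is after the reduction from 200 to 52 patients recorded in Protocol 5.0, in a study meant to inform reimbursement decisions (Protocol 7.0).

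**Working it through.** **Inputs, all from Protocol 9.5**

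- 52 recruited, "accounting for a 10% dropout rate": 52 × 0.9 = 46.8, so 46 to 47 evaluable.
- Two-sided alpha 0.05.
- First statement: null 0, mean -0.21, SD 0.5.
- Second statement: null -0.22, mean -0.5, SD 0.7.

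**Formula.** For a one-sample (paired) t-test, d = |mean − null| / SD. The non-centrality parameter is d × √n, with n − 1 degrees of freedom. Power is the probability that a non-central t variable with this parameter exceeds the two-sided 5% critical value (2.01 at n = 46 or 47).

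**Step 1: reproduce the first statement.** d = 0.21/0.5 = 0.42. At n = 47 the non-centrality is 0.42 × √47 = 2.88. Power is 79.6% at n = 46 and 80.5% at n = 47. The stated 80% is reproduced, so the method matches the sponsor's.

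**Step 2: apply it to the second statement.** The distance is 0.5 − 0.22 = 0.28, so d = 0.28/0.7 = 0.40. At n = 47 the non-centrality is 0.40 × √47 = 2.74.

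| Test of mean change against -0.22 | n = 46 | n = 47 | n = 52 (no dropout) |
|---|---|---|---|
| t-test, two-sided 0.05 | 75.6% | 76.6% | 80.8% |
| Normal approximation, two-sided 0.05 | 77.4% | 78.3% | 82.2% |
| t-test, one-sided 0.05 | 84.8% | 85.5% | 88.5% |
| Normal approximation, one-sided 0.05 | 85.7% | 86.4% | 89.2% |

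The most generous variant, with no dropout, a one-sided test and the normal approximation, stops at 89.2%.

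**Step 3: look for the source of 99%.** Keep the mean and SD but set the null to 0. Then d = 0.5/0.7 = 0.714, the non-centrality at n = 47 is 4.90, and power is 99.7% (n = 46) or 99.8% (n = 47). This is the simplest explanation found.

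**Step 4: what 99% against -0.22 would take.** With mean -0.5 and SD 0.7, 117 evaluable patients are needed, or 117/0.9 = 130 enrolled. At 46 to 47 evaluable, it would take an SD of about 0.43 to 0.44, or a mean of about -0.67.

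**Step 5: compare with the planned analyses.** No planned analysis uses -0.22 as a null value for the mean. The statistics listed in SAP 5.3 (mean, SD, minimum, maximum, median, quartiles) do not include a confidence interval, and SAP V0.4 records that quartiles replaced it. SAP 2.1 still allows either. Table 3.1 as described in SAP 5.3 would therefore not directly show whether the mean change excludes -0.22.

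**The case against.** **Another reading.** The sentence might mean that, if the true effect is as large as -0.5, which is beyond the clinically meaningful threshold, then the planned test against zero will be significant with 99% power. On that reading the number is right and only the bracket misleads. This is the weaker reading: the parallel bracket in the preceding sentence states the null, and the second bracket would then have no function. Even so, the text would need rewording.

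**The cause is inferred.** The documents do not show the calculation. A zero null gives 99.7% to 99.8% rather than exactly 99%, and a mistyped mean or SD cannot be excluded. This stands, but the mismatch does not depend on its cause.

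**Limited consequence.** The 52 patients rest on the first statement, which is correct. The second changes no sample size, test or decision rule, and no test against -0.22 is planned. All of this is true and limits the reach of the error. It does not make a wrong power figure acceptable in the two places where the protocol justifies its size.

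**The remedy could overreach.** A test against -0.22 would be a new hypothesis, and the SAP moved towards quartiles and the Wilcoxon test because normality was violated. The 76% is likewise a t-test figure. The added analysis is therefore needed only if the claim is kept.

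**Conclusion.** The concern holds. On the protocol's own assumptions (mean -0.5, SD 0.7, two-sided 0.05, 52 enrolled, 10% dropout, t-test), power to show a mean change beyond -0.22 is 75.6% to 76.6%, not 99%. The risk of missing that target is about 24% rather than 1%. No variant that keeps the stated null, mean and SD reaches 90%. The figure is also attached to a comparison that neither document plans to make. That the sponsor computed power against zero is a likely explanation, not an established one. The error is confined to the second power sentence in Protocol 9.5 and its copy in the Abstract. The primary test against zero and its 80% power are sound.

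**What to change.** In Protocol 9.5 and the Abstract, do one of the following.

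1. **Keep and correct.** Suggested wording: *With 47 evaluable patients, power is about 76% to show a mean change below -0.22 (mean -0.5, SD 0.7, two-sided 0.05), and more than 99% to show a mean change below zero under the same assumptions.* Then add the matching analysis to Protocol 9.7.4 and SAP 5.3: a one-sample t-test of the mean change against -0.22 or, equivalently, whether the upper limit of the two-sided 95% confidence interval lies below -0.22. SAP 5.3 would have to report that interval.
2. **Delete** the -0.22 power claim. No analysis then needs to be added.

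If the sponsor meant a test against zero all along, the bracketed condition should say so and the reference to a significant, clinically meaningful improvement should go.

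The cost is one sentence in two places and, under the first option, one further line of analysis. No extra patients are needed. The stated figure becomes less favourable.

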### 5.3 Analysis Plan for Primary Objectives

The objective of the primary endpoint analysis will be to demonstrate that treatment with adalimumab improves functioning as measured by the HAQ DI score in subjects with RA following treatment initiation (i.e. baseline).

- The changes in HAQ DI score at 12 and 24 weeks after the initiation of adalimumab will be presented (Excel Table 3.1); these changes will be summarized as the mean, SD, minimum, maximum, median, Q1, Q3; as well as the number and percent of patients achieving a clinically meaningful improvement on the HAQ DI, as defined by a -0.22 point improvement or greater. In addition, the mean or median change will be tested with a paired t-test or paired Wilcoxon signed-rank test without adjusting for baseline disease severity; for sensitivity analysis, the mean change will be analyzed using ANCOVA adjusting for baseline disease severity.
- The change in HAQ DI score at 24 weeks after the initiation of adalimumab (mean, SD, minimum, maximum, median, Q1, Q3), in those patients continuing on adalimumab (observed population) will be compared with those patients not continuing on adalimumab (withdrawal population). The mean or median changes in these two groups will be compared using an independent t-test or paired Wilcoxon signed-rank test listed in the table (Excel Table 3.2).

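### Protocol 9.5 claims 99% power to show a mean HAQ DI change below -0.22, but no planned analysis compares the mean change with -0.22

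*Protocol*

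**What the plan says.** Protocol 9.5, repeated in the abstract, makes two power statements for the same 52 patients.

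- The first is "The planned sample size provides 80% power for detecting a statistically significant improvement in HAQ-DI", that is, a mean change below 0, assuming a mean "of -0.21 and a standard deviation of 0.5".
- The second is 99% power for "detecting a statistically significant clinically meaningful improvement in HAQ-DI", that is, a mean change below -0.22, assuming a mean of -0.5 and an SD of 0.7.
- Both are "at two-sided significance level of 0.05" and "accounting for a 10% dropout rate".

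The primary analysis in Protocol 9.7.4 reads: "This change will be summarized as the mean and 95% confidence interval and will be tested with a paired t-test". SAP 5.3 says that "the mean or median change will be tested with a paired t-test or paired Wilcoxon signed-rank test without adjusting for baseline disease severity". The ANOVA (protocol) or ANCOVA (SAP) adjusting for baseline severity is a sensitivity analysis.

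In the analysis sections (Protocol 9.1, 9.7.5; SAP 2.2, 5.3), -0.22 is used only to classify individual patients as improved or not at weeks 12 and 24. The result is a number and percentage without a test. SAP section 4 rests the HAQ DI sample size on -0.21 alone and has no -0.22 scenario.

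The protocol plans a 95% confidence interval for the mean change. SAP 2.1 makes it an alternative to the median with quartiles. SAP 5.3 lists mean, SD, range, median and quartiles, and no interval.

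**The concern.** Power is a property of a test. Protocol 9.5 specifies a null (-0.22), an effect, an SD and a power for a second hypothesis about the mean, but the analysis sections have no corresponding test or criterion. A reader of 9.5 would expect the final report to say whether clinically meaningful mean improvement was shown. Nothing in the plan says how that would be decided.

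Meanwhile the primary test, whose aim is to demonstrate improved functioning, can succeed on a mean change that 9.5 would not call clinically meaningful. The effect assumed for the first power statement, -0.21, lies just short of the threshold itself. The results are meant for payers and health authorities in China, who may well ask whether the change is clinically meaningful as well as whether it differs from zero.

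**Working it through.** **Inputs (Protocol 9.5).** Enrolment: "Approximately 52 patients diagnosed with RA will be recruited". Dropout 10%, so 52 × 0.9 = 46.8; I use n = 47 evaluable. Two-sided alpha 0.05, so the critical value is t(0.975, 46) = 2.013. Scenario 1: mean -0.21, SD 0.5, null 0. Scenario 2: mean -0.5, SD 0.7, null -0.22. Power comes from the noncentral t distribution with noncentrality |mean − null| / (SD/√n).

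**Step 1. Reproduce the plan's power figures.**

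| Scenario | Null | Noncentrality | Power, n = 47 | Stated |
|---|---|---|---|---|
| -0.21, SD 0.5 | 0 | 0.21 / 0.0729 = 2.88 | 80.5% | 80% |
| -0.5, SD 0.7 | -0.22 | 0.28 / 0.1021 = 2.74 | 76.6% | 99% |
| -0.5, SD 0.7 | 0 | 0.50 / 0.1021 = 4.90 | 99.8% | – |

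The first statement reproduces. The second does not. Power against -0.22 is 75.6% at n = 46 and 80.8% at n = 52 with no dropout. The most favourable variant tried (one-sided, normal approximation, n = 52) gives 89.2%. The stated 99% is close to what the same mean and SD give against a null of zero. Reaching 99% against -0.22 would take 117 evaluable patients, or 117/0.9 = 130 enrolled.

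**Step 2. Smallest observed improvement that is significant against zero** = t × SD/√n.

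- SD 0.5: 2.013 × 0.5/√47 = 0.147
- SD 0.7: 2.013 × 0.7/√47 = 0.206

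Both are less than 0.22.

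**Step 3. Observed mean needed for the whole 95% interval to lie below -0.22.**

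- SD 0.5: -(0.22 + 0.147) = -0.367
- SD 0.7: -(0.22 + 0.206) = -0.426

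For example, an observed mean of -0.21 with SD 0.5 has the interval -0.21 ± 0.147, or -0.357 to -0.063. It is significant against zero but does not exclude -0.22.

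**Step 4. How often the two questions part company** (simulation, 200,000 normal samples of n = 47 per scenario).

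| True mean, SD | Significant against 0 | Significant, but observed mean short of -0.22 | Whole 95% CI below -0.22 |
|---|---|---|---|
| -0.21, 0.5 | about 80% | 36% | 1.8% |
| -0.5, 0.7 | 99.8% | 0.1% | 77% |

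In the first row the true mean does not reach -0.22, so a low rate in the last column is what a valid comparison should give. The row shows how often the planned success criterion can be met without an observed mean that reaches the threshold. In the second row the gap nearly disappears.

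**The case against.** A reader might infer that the plan can never show clinically meaningful mean improvement. The documents do not support that. The protocol's 95% interval would show it if its upper limit fell below -0.22, and even under SAP 5.3 the interval can be rebuilt from the reported mean and SD with the number analysed. What is missing is a stated rule and, in SAP 5.3, the interval itself.

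A reader might also infer that the study was sized for the -0.22 hypothesis. It was not. The 52 patients follow from -0.21 against zero; the -0.22 sentence is an added claim about the same sample, and SAP section 4 does not mention it.

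The strongest counter-argument is that no test against -0.22 was ever intended. No objective in either document claims clinically meaningful improvement of the mean, clinical relevance is addressed by the responder percentage, and the 99% fits a null of zero. On that view the fault is one mis-stated power sentence. This is plausible, and it is why deletion is an acceptable repair. It does not remove the mismatch: 9.5 does apply -0.22 to the mean, names it as a hypothesis and gives it a power.

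Finally, the 36% should not be read as the study's expected behaviour. It belongs to the less favourable of the plan's two scenarios.

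**Conclusion.** The point holds as an inconsistency between the power statement and the analysis plan. Protocol 9.5 claims power for a comparison that neither document makes, and the claimed 99% is about 77% on the stated inputs. The primary test against zero remains valid and its 80% reproduces, but its success alone does not establish a mean improvement beyond 0.22: it can be met at an observed improvement of 0.147 (SD 0.5) or 0.206 (SD 0.7).

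These figures assume 47 evaluable patients, the SDs given in 9.5 and roughly normal changes. The SAP document history records that normality was violated, so the Wilcoxon route may be the one used. That makes it more likely that no interval for the mean is reported.

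**What to change.** Choose one of two repairs.

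**(a) Keep the hypothesis and give it an analysis.**

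- In SAP 5.3 and Table 3.1, restore the 95% confidence interval of the mean week-24 change, whichever test is used.
- In SAP 5.3 and Protocol 9.7.4, state that if, and only if, the week-24 test against 0 is significant, clinically meaningful mean improvement is concluded when the upper 95% limit is below -0.22. Because the order is fixed, a prespecified step needs no alpha adjustment.
- If the Wilcoxon route is taken, apply the signed-rank test to (change + 0.22) instead. Word the conclusion as one about the typical (median) change, since that test does not address the mean directly.
- In 9.5 and the abstract, replace 99% by about 77% (mean -0.5, SD 0.7, n = 47).
- Label the step post hoc if it is added after the data have been seen. This is likely: Protocol 6.0 planned data collection to end on 30 June 2018, and the SAP versions of December 2018 and May 2019 already refer to violated normality.

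**(b) Drop the hypothesis.** Delete the -0.22 power sentence from 9.5 and the abstract, and make no claim of clinically meaningful mean improvement. The responder percentages remain as description.

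The cost of (a) is a few sentences and one line in Table 3.1, with the risk that the study is significant against 0 yet supports no claim of clinical meaning. The cost of (b) is giving up that claim from the start.
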